Temporal Sequence of Study Procedures. Patients will be identified by providers working in VA mental health programs and primary care settings. The prescribing provider will alert potential patients to the study and introduce interested patients to the Research Coordinator (RC) or other study staff at each site. The handoff from the provider to the study staff will be by secure electronic means, a phone call or in person. Sites are encouraged to have a back-up telephone contact plan so that someone on the research staff is always available to providers for phone access. This could be a backup RC or the LSI or a beeper or cell phone. Alternatively, if the patient wants to return for a later appointment for consent and randomization, this pathway should also be worked out locally so that no patient is left without contact or potentially doesn't receive treatment because of the study procedures. If providers are unable to contact staff, they should not delay treatment and thus should forgo subject referral. The prescribing provider will complete a referral form which includes confirmation of some inclusion and exclusion criteria and the responses to treatment decisions. Potential participants are those who are about to undergo antidepressant treatment for MDD or be switched from a current antidepressant to a new one. The study staff will describe the study to the patient and initiate the informed consent process. After consent, a brief baseline assessment will be conducted by the study staff to establish eligibility and to collect baseline data prior to randomization. We will keep track of the number of study referrals and will collect the following research data for those who do not consent: name, SSN, age, sex, race, and ethnicity. Name and SSN are tracked for those who do not consent so that research coordinators can determine if a subject has already been referred to the project (re-referral), and whether outcomes from an earlier referral impact eligibility. The design of the study will mimic routine clinical care, which will minimize the research burden and maximize the ecological validity of the trial. While every attempt will be made to complete the baseline visit within 60 minutes on the day of the clinical visit to allow randomization to occur rapidly and not delay prescribing, the patient will be given the option to return to the clinic on another day to give consent (e.g., to discuss potential participation with family) and complete the baseline assessment.

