 - iv. Functional assessment The Veterans RAND 12-item Health Survey (VR-12) is a widely used measure of quality of life [44]. The VR-12 subscales measure physical and mental functioning. The scale is a publicly available version of the MOS SF-12 instrument [45, 46]. The measure will be administered at baseline and all follow-up assessments. The results of the baseline VR-12 assessment will be placed in the EHR.
 - v. Alcohol use The Timeline Follow-back (TLFB) [47] will be used to estimate past 7-day drinking at baseline and at each follow-up visit. The TLFB uses a retrospective calendar method to measure daily alcohol use. We chose a 7-day TLFB window because it is easily ascertained and provides a snapshot of recent drinking that reflects average alcohol consumption. The TLFB is the most widely used outcome measure in alcohol studies [48]. The results of the baseline TLFB assessment will be placed in the EHR.
 - vi. Illicit drug use The NIDA-Modified ASSIST was adapted from the Alcohol, Smoking and Substance Involvement Screening Test (ASSIST). It was developed, validated, and published by the World Health Organization (WHO) as a screening tool for substance use [49]. This self-report questionnaire will be

completed at baseline to describe the patient population. The results of the baseline ASSIST assessment will be placed in the EHR.

- vii. Treatment satisfaction We will use two questions that ask about the quality of care received and the ability to receive the services desired. The questions are adapted from the 28-item version of the Mental Health Statistics Improvement Program (MHSIP) Consumer Survey [50]. We have used these two questions for 10 years in our Primary Care Mental Health Integration (PCMHI) program. Because raters assessing satisfaction with study participation at each follow-up visit are blinded to treatment assignment, we will be unable to ask specifically about the PGx testing using the MHSIP. The measure will be done at each follow-up assessment.
- viii. Receiving results at four weeks the local research coordinator will ask if patients in the intervention group were given a copy of the results. We will ask the control group at week 36.
- ix. Current smoking At each visit, we will record the average number of cigarettes smoked daily over the past week. The results of the baseline smoking assessment will be placed in the EHR.

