- x. Demographics Patient will self-report basic demographic information: sex, race, branch of military, works status, marital status, and ethnicity. We will also record the patient's birthdate, address and phone number as part of a tracking data base but these data will not be part of the analytic data set.
- xi. Antidepressant adherence This is a self-report assessment of the patient's adherence to medications during the prior week. The measure will be administered at all follow-up assessments.
- xii. Structured adverse effects questionnaire The Assessment of Side Effects is a semi-structured interview designed to assess and track the course and severity of adverse effects including headache, nausea or vomiting, diarrhea, constipation, and sexual dysfunction. The measure will be done at each follow-up assessment. Designations of mild, moderate, and severe will be used to grade the severity of any adverse effects. The measure will be administered at all follow-up assessments.
- xiii. Treatment history By self-report, we will obtain the lifetime information about treatment exposures including psychotherapy, and self-reported effectiveness of the most helpful treatment. This will provide information on the chronicity of depression and a proxy measure of treatment resistance. It will be obtained at baseline.
- xiv. Lifetime psychiatric diagnoses The MINI International Neuropsychiatric Interview (MINI) [51] will be used to screen for lifetime mania and psychotic symptoms, panic disorder, antisocial personality disorder, and drug and alcohol dependence. It will be administered at week 4 by the local research coordinator/staff. If missed at the 4 week interview, the questions will be asked virtually.
- xv. Nutritional assessment by self-report we will record selected nutraceuticals and foods use that have been associated with depression and/or medication metabolism. This is not a standardized assessment but rather developed for this study. The responses will be used by the discovery core to combine with genetic data to refine analyses related to outcomes and new genetic markers.
- xvi. Treatment received outside the VA This instrument will be used to collect information on all non-VA health services received, including ER, inpatient, and outpatient care. The measure will be administered at baseline and all follow-up assessments.

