5.6.b. Patient and provider use of PGx results (Hypothesis #2). For each provider-patient dyad in the trial, we will use the results of the genetic test to classify each medication prescribed by the provider to that patient as green, yellow, or red, thus creating an ordinal measure for each time the provider prescribes a medication. Our primary response for Hypothesis #2 will be the correspondence between the study-period prescription for the provider-patient dyad across the randomized groups. We will compare the groups on the probability of receiving medications of the three types (red, yellow, green) using mixed effects ordinal regression model, including random intercepts for providers.

5.6.c. Secondary Responses (Hypothesis #3). We will use generalized linear regression models to evaluate secondary outcomes, using the same covariates as above: a binary indicator for intervention group, and variables for site, provider, and depression severity. Regression models will include random effects to accommodate correlations due to repeated measures and nesting of patients within providers.

Secondary analyses will include an examination of the longitudinal trajectories of PHQ-9 summaries of depression severity across the intervention phase. These models will use the overall PHQ-9 score as a response, yielding a set of continuous (possibly skewed) repeated measures. These responses will be analyzed using mixed-effects linear models (or mixed-effects gamma models, depending on the degree of skewness). We will compare the groups on functional improvement, using the mental health component of the VR-12 score, with analogous generalized linear mixed effects models appropriate to the response distribution.

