Dropout and Missing Data. We anticipate that there will be dropout from the study as well as intermittent missing data, in particular for the patient outcome responses of Hypothesis #1, while some Veterans may not receive an antidepressant prescription in the 30-days post-randomization for Hypothesis #2. The mixed-effects models described above for Hypothesis #1 make use of all available responses, can accommodate the heterogeneity of response times caused by intermittent missing data, and provides valid estimates and hypothesis tests under an assumption of ignorable missingness. To assess the sensitivity of our conclusions to this assumption, we will extend the mixed-effects models to consider inverse probability-weighted selection models and pattern mixture models [22]. We will perform these analyses under a range of different prediction models and assess the sensitivity of the results. For Hypothesis #2 we will use a multiple imputation approach. [32-33]

Secondary Hypotheses.

Secondary Responses (Hypothesis #3). We will compare the intervention groups on their repeated depression response outcomes using mixed effects logistic regression models, as described for primary Hypothesis #1. For the PHQ-9 summary score of depression severity, we will use mixed-effects linear models.

We will use generalized linear regression models to compare the groups on side effect rate, treatment adherence rate, and functional improvement. Regression models will include random effects to accommodate correlations due to nesting of patients within providers, and repeated measures (where necessary).

Rationale for amendments made– Number of outpatient visits was removed from the secondary outcomes as there are no standards for an acceptable frequency of outpatient visits, particularly when comparing specialty mental health care and primary care.

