We will also compare the groups on the rates of side effects that are moderate or severe. Side effects may be more plausibly related to serum antidepressant levels and thus PGx results than depressive symptoms. The data will include binary ratings of presence of moderate to severe headache, nausea or vomiting, diarrhea, constipation, and sexual dysfunction at weeks 4, 8, 12, 18, and 24. We will use a mixed-effects logistic regression model to test whether there are differences in the probabilities of moderate or severe side effects between the two intervention groups. We will compare the groups on functional improvement, using the mental health component of the VR-12 score, with analogous generalized linear mixed-effects models appropriate to the response distribution.

We will compare differential outcomes by randomized group on adherence rates. For Hypothesis #1, there are two types of adherence to be considered. First, a provider/patient dyad in the intervention group may not use a recommended medication (this is the focus of Hypothesis #2 with the analytic plan described above). The second form of adherence is whether the patient is actually taking their medication as prescribed. We assess medication adherence using electronic health record data on prescriptions filled. From the prescriptions filled data, we will calculate an antidepressant medication possession ratio. For each Veteran, we will create a binary variable, indicating whether they filled medication prescriptions for at least 80% of days through the 24-weeks treatment period, and compare the groups on this outcome using logistic regression models, as described above.

Rationale for amendments made– The above section on adherence was amended from the methods paper to separate the analysis for Hypothesis #2 and to further clarify medication adherence as a secondary outcome. Originally proposed was a self-reported variable on adherence. However, during the trial it was apparent that the validity of this assessment was suspect as patients often didn't remember their medications and had difficulty assessing adherence to specific medications. Prescription fill rates is considered a more reliable method for ascertaining availability of medication though it does not assess whether the patient has taken the medication. Below we also clarify that the proposed adherence by treatment interaction analysis was to be explored in secondary manuscripts.

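### The SAP does not say how baseline VR-12 enters the functional-improvement model; naming it as a covariate gains precision from data already collected

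*SAP*

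**What the plan says.** **VR-12.** Protocol 5.5.b (Functional assessment) and Table 2 schedule VR-12 at baseline and at every follow-up, and the protocol adds that "The results of the baseline VR-12 assessment will be placed in the EHR". Protocol 5.6.c (Secondary Responses) lists the Hypothesis #3 covariates as "a binary indicator for intervention group, and variables for site, provider, and depression severity".

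The SAP, under Secondary Hypotheses, does not repeat that list. It says "We will use generalized linear regression models to compare the groups on side effect rate, treatment adherence rate, and functional improvement", adds random effects for provider nesting and repeated measures, and then says "We will compare the groups on functional improvement, using the mental health component of the VR-12 score", with models described only as analogous to those before. It does not define improvement as a follow-up score, a change from baseline or a baseline-adjusted score. For Hypothesis #1, by contrast, the SAP puts baseline PHQ-9 in the model by name.

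**Side effects.** Protocol 5.5.b (Structured adverse effects questionnaire) says "The measure will be done at each follow-up assessment. Designations of mild, moderate, and severe will be used to grade the severity", and the baseline cell in Table 2 is blank. The SAP endpoint is prevalence at weeks 4, 8, 12, 18 and 24: "The data will include binary ratings of presence of moderate to severe headache", followed by the other listed symptoms. Protocol 5.2 makes eligible both patients about to start an antidepressant and those about to "be switched from a current antidepressant to a new one".

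**The concern.** A baseline measurement of the outcome is usually its strongest single predictor. The trial collects it for VR-12, but no covariate list mentions it. An analyst following the protocol's list literally would fit depression severity and leave out baseline function. An analyst reading improvement as change would subtract the baseline. A third might adjust for it. These analyses differ in precision, and the plan does not choose between them before the data are seen. At stake is the width of the confidence interval for a secondary outcome.

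For side effects, there is no day-0 rating and patients already on an antidepressant can enter. A moderate headache or sexual dysfunction recorded at week 4 may therefore pre-date the study prescription, and the reported rates could be misread as treatment-emergent.

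**Working it through.** **The plan's own figure.** Protocol 5.6.i takes 2000 patients, ten per provider and a provider ICC of 0.05. The design effect is 1 + 9 × 0.05 = 1.45, and 2000/1.45 = 1379, as stated. The documents give no SD, correlation or power for VR-12, so every correlation below is an assumption. Correlations involving PHQ-9 are absolute sizes, since the two scales run in opposite directions. I read depression severity in the protocol's list as baseline PHQ-9. The percentage cuts do not depend on 1379.

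**Gain beyond baseline PHQ-9, one set of values.** Assume correlations with follow-up VR-12 of 0.5 (baseline VR-12) and 0.35 (baseline PHQ-9), and 0.6 between the two baselines.
- PHQ-9 alone: R² = 0.35² = 0.1225, residual 0.8775.
- Both: R² = (0.25 + 0.1225 − 2 × 0.5 × 0.35 × 0.6)/(1 − 0.36) = 0.1625/0.64 = 0.254, residual 0.746.
- Ratio 0.746/0.8775 = 0.85: a 15% cut in variance, about 8% in standard error.

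**Range at week 24.** Let r be the correlation of baseline with follow-up VR-12. Keep 0.6 between the baselines, and let PHQ-9 predict follow-up VR-12 only through baseline VR-12 (correlation 0.6r). Residual variance is 1 − (0.6r)² with PHQ-9 alone and 1 − r² with baseline VR-12.

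| r | PHQ-9 only | VR-12 added | Cut |
|---|---|---|---|
| 0.3 | 0.968 | 0.910 | 6% |
| 0.5 | 0.910 | 0.750 | 18% |
| 0.7 | 0.824 | 0.510 | 38% |

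**Average of five visits.** With the same r between all visits, the variance is (1 + 4r)/5 less the same squared terms. The cuts are 14% (0.350 against 0.408), 31% (0.350 against 0.510) and 54% (0.270 against 0.584).

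**If improvement means a change score.** The week-24 variance is 2 − 2r for change and 1 − r² with baseline as covariate, a saving of (1 − r)/2: 35%, 25% and 15% for r = 0.3, 0.5 and 0.7. PHQ-9 is left out of this comparison.

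**Detectable difference.** Take 1379 × 0.8 = 1103 after the plan's 20% loss, 80% power and 5% two-sided (assumed; no secondary alpha is stated). With no baseline covariate it is (1.96 + 0.84) × 2/√1103 = 0.169 SD. Multiplying by the square root of the residual variance gives, for PHQ-9 only and then with VR-12 added:
- r = 0.3: 0.166 and 0.161 SD
- r = 0.5: 0.161 and 0.146 SD
- r = 0.7: 0.153 and 0.120 SD

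**Side effects, illustration only.** Assume new-onset rates of 15% and 10%, and a share b with symptoms that pre-date treatment and persist equally in both arms. The observed rate is b + (1 − b)q. For b = 0, 10, 20 and 30% the difference is 5.0, 4.5, 4.0 and 3.5 points, and the odds ratio is 0.63, 0.76, 0.83 and 0.86. The documents give neither b nor these rates.

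**The case against.** The SAP never says that VR-12 is analysed without its baseline. Improvement can be read as change from baseline, and the word analogous could carry over an own-baseline term like the PHQ-9 term in Hypothesis #1. This stands. A reader might infer that baseline VR-12 is excluded from the model, but the documents support only that its use is unspecified.

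A comparison with a model holding no baseline information would flatter the gain, because the protocol already lists depression severity. This also stands, and it is why the PHQ-9-adjusted figures lead here.

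A reader might infer bias between arms. The documents do not support that: randomization is within provider, so baseline function and pre-existing symptoms balance on average.

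On side effects, it is tempting to add a baseline questionnaire and count only new or worse symptoms. Three points tell against that:
- Table 1 planned all 2000 patients by 30 September 2020, and the SAP was finalized on 16 August 2021. Recruitment may have run past plan, but a new baseline rating would reach few patients or none.
- Current burden at each visit is a legitimate endpoint. A new-or-worse rule gives no credit when a guided switch relieves an existing side effect.
- The interview's wording, including any attribution to medication, is not in the documents. Nor is the share of patients who are switching, so it cannot be called large.

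**Conclusion.** The VR-12 point holds as a specification gap. The baseline is collected, no listed covariate set contains it, and the plan does not say how it is used. Naming it as a covariate improves precision whether improvement was meant as a follow-up score or as change. With baseline PHQ-9 in the model, the further cut in residual variance is about 15% at the single set of assumed correlations, and about 6% to 38% at week 24 over r = 0.3 to 0.7. The size rests wholly on those assumptions; the direction does not.

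The lack of a pre-treatment side-effect rating is real, but it is a limit on interpretation. It supports calling the rates prevalence that may include pre-existing symptoms, and nothing stronger.

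**What to change.** Add one sentence to the SAP under Secondary Hypotheses (Hypothesis #3), dated and approved before the analysis: the mixed model for the VR-12 mental component score includes the baseline value of that score as a covariate. The same sentence should say whether the protocol's depression-severity covariate is kept, since the SAP does not repeat that list. Once baseline VR-12 is in a linear model, follow-up score and change score give the same group contrast, so the ambiguity over improvement no longer matters. The cost is one line and one model parameter, with no new data.

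For side effects, leave Table 2 and the endpoint as they are. State in the report that the week 4 to 24 figures are the prevalence of moderate or severe symptoms, that no pre-treatment rating was taken, and that symptoms present before the study prescription may be included.

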5.0 Study Procedures

5.1 Study Design

The study is a two-arm, 24-week, parallel-groups comparison of patient/provider dyads (n=2000), which will be randomly assigned to receive the results of the PGx battery at the time of randomization (i.e., the intervention group) or receive the results after 6 months of treatment as usual (i.e., the delayed results group). The genetic test results are designed to assist the patient/provider dyad in making a shared decision as to the appropriate antidepressant. There are many additional factors that can influence that decision and the provider/patient dyads are not obligated to follow the recommendations in the genetic test report but rather are encouraged to use the results to inform shared decision making.

The study intervention. The intervention for this study is the delivery of genetic test results that reflect pharmacokinetic and pharmacodynamic effects of specified genetic markers. The choice and dose of the antidepressant to be prescribed to each patient is left to the provider and patient, though we will recommend to the provider that he or she carefully consider the genetic test results prior to selecting a medication and dose. For the trial, we will use the commercially available GeneSight[™] psychotropic panel from Assurex Health. This product, which combines genetic markers related to pharmacokinetics and pharmacodynamics, has the greatest market penetration of any genetic tests for MDD treatment.

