Patient Education. Patients will have access to a number of educational materials available for providers to assist in partnering with patients in the decision process. At the time of randomization, an instruction sheet will be provided to the patient that reminds them of the arm they were assigned. In the intervention arm, this instruction sheet includes a reminder to call their provider if they haven't heard back within 10 business days so that medication can be started. Educational resources also include brochures about the test result, and access to Assurex's website which is publicly available. A short whiteboard video will also be developed and available on the study website available to the public that explains the genetic test. In addition, patients have access to Assurex's call center (toll free) which will review results with patients at their request. This is voluntary and only initiated by the Veteran. The call number is printed on the test result along with the subject's sample acquisition ID number that allows the company's call center to identify the Veteran. This optional service is a standard part of Assurex's product.

There are no study medications prescribed as part of this study. The antidepressants used will be limited to those prescribed by an authorized VA provider and only informed by the genetic results in the intervention arm. The genetic testing is not regulated under an Investigational New Drug (IND) or Investigational Device Exemption (IDE) process.

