In secondary manuscripts, we will assess the sensitivity of the results of the analyses described above to non-adherence, by extending the models described above for primary and secondary outcomes using instrumental variable approaches. Here, the instrumental variable is randomization that, under some conditions, will control for unmeasured bias (due to self-selection to adhere or not) when estimating the relative effects of the medications in those who adhere to their assigned medication. Results will use data from all patients who show various degrees of adherence as measured by the availability of medication or adherence to the PGx recommendation and will yield estimates of the intervention effects that would have been seen in a study with full adherence. For a single overall measure of adherence, we will use the methods of Nagelkerke et al. [25]; if there is sufficient within-patient variation across time in adherence, we will use the longitudinal methods of Small et al. [26].

Change in prescribing in delayed results group post-intervention (Hypothesis #4). At the conclusion of the six-month intervention phase of the trial, the PGx battery results are returned to the providers (and patients) in the delayed group. The primary outcome for Hypothesis #4 will be the ordinal variable corresponding to prescriptions written in the first 30 days after return of results. We will use a mixed-effects ordinal regression model to test whether the probabilities of red and yellow medications decrease from before the release of the PGx results through the 30 days after release.

Further descriptive analyses:

Rationale for amendments made– Not specified in the methods paper are descriptions of the impact of the study on routine clinical care. To describe potential delays in care associated with the time of collecting and releasing PGx results, we will present data on the time from randomization to the release of the PGx results in the intervention arm. Descriptive data of participating providers and randomized participants will also be provided in the primary outcomes.

References:

2. Trivedi, M.H., et al., *Evaluation of outcomes with citalopram for depression using measurement-based care in STAR*D: implications for clinical practice*. Am J Psychiatry, 2006. **163**(1): p. 28-40.

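### The planned adherence instrumental-variable analysis has no assigned medication to work on, and with medication availability as the exposure randomisation does not identify a full-adherence effect

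*SAP*

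**What the plan says.** The adherence text in the SAP (Secondary Hypotheses) and in Protocol 5.6.h has four parts.

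- Instrument: "the instrumental variable is randomization that, under some conditions, will control for unmeasured bias". The conditions are not listed.
- Target: "estimating the relative effects of the medications in those who adhere to their assigned medication".
- Exposure, left as two alternatives: "as measured by the availability of medication or adherence to the PGx recommendation".
- Claim: the analysis "will yield estimates of the intervention effects that would have been seen in a study with full adherence".

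Protocol 5.1 describes a different kind of trial. "The intervention for this study is the delivery of genetic test results"; "The choice and dose of the antidepressant to be prescribed to each patient is left to the provider and patient"; and "There are no study medications prescribed as part of this study". Under Protocol 5.5 (Visit 1), delayed-arm dyads start the antidepressant agreed before randomisation, so both arms are treated. Protocol 5.2 encourages providers in the intervention arm to use the report for the target dose as well as the drug.

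The SAP separately compares the arms on a binary fill measure (prescriptions filled for at least 80% of days over 24 weeks) and notes that fills do not show that the drug was taken. It confines the instrumental-variable work to secondary manuscripts. Protocol 5.6.h treats it as a sensitivity analysis and expects adherence adjustments to be small.

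**The concern.** The target is worded for a trial that randomises a drug, where randomisation shifts drug exposure and is assumed to act only through it. Here randomisation shifts information. The report is meant to work by changing which drug is chosen (Hypothesis 2) and possibly its dose. A patient can fill at the same rate in either arm and still do better because a different drug was chosen. If the arm effect on remission is attributed to possession, the drug-choice effect is credited to the wrong exposure.

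What is at stake is the label on a published estimate. A figure presented as the effect under full adherence would be neither the effect of possession nor the effect of the report in full adherers. The exposure is also left open between two quite different quantities, so it could be chosen after results are seen.

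**Working it through.** The documents give no figure for this analysis. The only stated size for how far randomisation may move an exposure is the Hypothesis 2 detectable odds ratio, so that is reproduced first. Below, a simple ratio (arm difference in remission divided by arm difference in exposure) stands in for the cited methods.

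**1. The SAP's odds ratio.** Inputs from the SAP: N = 2000, shares 40/40/20, two-sided 2.5%. With the proportional-odds variance, V = N(1 − Σp³)/12 = 2000 × (1 − 0.064 − 0.064 − 0.008)/12 = 144. Detectable log odds ratio = (2.241 + 0.842)/√144 = 0.257, an odds ratio of 1.293. Power at 1.29 is 79.2%. The SAP's figure reproduces.

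**2. Exclusion, with availability as the exposure.** All inputs in this step are assumed. Possession raises remission by 10 points; a concordant drug adds 5 points among those who possess it; concordance is 37% delayed and 47% intervention; possession is 50% delayed and 50% + d intervention.

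Arm effect = 0.10d + 0.05 × [(0.50 + d) × 0.47 − 0.50 × 0.37]

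| d | Arm effect | Ratio (arm effect / d) |
|---|---|---|
| 0.02 | 0.0020 + 0.05 × 0.0594 = 0.00497 | 0.249 |
| 0.05 | 0.0050 + 0.05 × 0.0735 = 0.00868 | 0.174 |
| 0.20 | 0.0200 + 0.05 × 0.1440 = 0.02720 | 0.136 |

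The true effect of possession is 0.10 + 0.05 × 0.37 = 0.1185 to 0.10 + 0.05 × 0.47 = 0.1235. The true effect of the report if everyone possessed the drug is 0.05 × (0.47 − 0.37) = 0.005. The ratio equals neither, even at d = 0.20, where the first stage is strong (F = 0.20²/(0.25/1000 + 0.21/1000) = 87). The failure does not depend on a weak instrument.

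**3. First-stage strength, availability.** F = d²/[p₀(1 − p₀)/1000 + p₁(1 − p₁)/1000], with 1000 per arm and no clustering. The delayed-arm fill rate p₀ (30 to 70%) and d are assumed. The ratio takes the SAP's 5-point remission effect.

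| d (points) | F | Ratio, in points |
|---|---|---|
| 0 | 0 | undefined |
| 2 | 0.8–1.0 | 250 (not possible for a risk difference) |
| 5 | 5.0–6.3 | 100 |
| 10 | 20–27 | 50 |

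The standard error must include first-stage error. At 60% filling, the remission difference has SE √(0.30 × 0.70/1000 + 0.35 × 0.65/1000) = 0.0209 and the fill difference √(2 × 0.6 × 0.4/1000) = 0.0219. By the delta method with zero covariance, SE = √(0.0209² + ratio² × 0.0219²)/d, which is about 293 points at d = 2 points and 61 at d = 5. Allowing for the 20% loss to follow-up and provider clustering would widen these.

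**4. First-stage strength, concordance.** The SAP's shares are split between the arms at a common odds ratio.

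| Odds ratio | Exposure | Delayed vs intervention | Difference (points) | F | Ratio for 5 points, in points |
|---|---|---|---|---|---|
| 1.29 (SAP) | green | 36.9% vs 43.1% | 6.1 | 7.8 | 82 |
| 1.29 (SAP) | not red | 78.0% vs 82.0% | 4.1 | 5.2 | 123 |
| 2 (assumed) | green | 31.8% vs 48.2% | 16.5 | 58 | 30 |

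The exposure that the report is meant to move can therefore be a weak or a strong instrumented exposure. Which of these applies will be known only from the data.

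**The case against.** **A near-zero denominator is not in the documents.** A reader might infer that randomisation hardly moves pill-taking and that the whole analysis collapses. No arm difference in fills is stated. Hypothesis 3 expects better adherence in the intervention arm, and Protocol 5.6.c allows that the delay could leave more of that arm untreated. Weakness is therefore an assumption, and at 10 points it disappears. This objection stands.

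**The full-adherence estimate is not lost under every reading.** Two exposures are named, and the second, adherence to the PGx recommendation, is usable. This stands too. The first could also be coded as having a report-guided drug available, which is zero by definition in the delayed arm; the denominator would then not be small. The SAP does not say so. That coding would need the further assumption that the report does nothing for patients below the fill threshold.

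**The ratio is a stand-in.** The SAP extends mixed-effects logistic models through two cited non-compliance methods, and how those behave with a weak instrument cannot be judged from these documents. The ratios above therefore show scale only and do not predict what would be published. The exclusion argument does not rest on them.

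**Much of the remedy is already planned.** Concordance is named as an exposure, prescriptions are graded from the PGx result for every dyad, and fills are compared by arm. That is correct, and it makes the change small.

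**It is a hedged sensitivity analysis.** True, and that sets the severity. However, the hedge on conditions is never spelled out, while the sentence promising "estimates of the intervention effects that would have been seen in a study with full adherence" carries no hedge.

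**Conclusion.** Wrong as written, at low severity. The stated target has no referent in this design. With medication availability as the exposure, coded alike in both arms, the exclusion restriction fails by design and randomisation does not identify a full-adherence effect at any first-stage strength. That conclusion needs only the protocol's own account of how the report is meant to work.

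Instrument weakness is a secondary and conditional point. It holds for availability if the arms differ by about 5 points or less, and for concordance near the SAP's odds ratio of 1.29. That odds ratio is a detectable effect and not a forecast. With either exposure, the protocol's expectation that adjustments will be small cannot be taken for granted: a 5-point effect becomes 82 points when divided by a 6.1-point difference in green prescribing.

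Even with concordance, the estimate applies to dyads whose drug choice the report changed, under exclusion and monotonicity. Exclusion is not automatic there, since the report may also guide dose. No primary or secondary hypothesis test depends on this analysis.

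**What to change.** In the SAP adherence section and Protocol 5.6.h:

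1. Remove medication availability as an instrumented exposure. Keep the by-arm comparison of fills that the SAP already specifies.
2. Define the exposure as concordance of the first-30-day prescription with the PGx result, graded from genotype in the same way in both arms. Fix the cut in advance (green versus other, or not red versus red).
3. Replace the assigned-medication and full-adherence wording with: effect among dyads whose drug choice was changed by the report.
4. State the exclusion and monotonicity assumptions, and say how dose guidance from the report bears on exclusion.
5. Report the first-stage difference and F, with a weak-instrument-robust interval.

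The cost is wording in two documents and the loss of one planned sensitivity analysis for secondary manuscripts. No new data are needed: the genotype-graded prescriptions are already required for Hypothesis 2.
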